### PROTOCOL INFORMATION

Date of Registration: \_\_\_\_\_ / \_\_\_\_\_ / \_\_\_\_\_

MD Name (last): \_\_\_\_\_

Date protocol treatment started: \_\_\_\_\_ / \_\_\_\_\_ / \_\_\_\_\_

Informed written consent:  YES  NO

(consent must be signed prior to registration)

Date Consent Signed: \_\_\_\_\_ / \_\_\_\_\_ / \_\_\_\_\_

PID # (to be assigned by WISER): \_\_\_\_\_

*Protocol Registrar can be contact by calling [contact] between 8:30 AM and 4:00 PM, Monday – Friday. Completed Eligibility Checklist and Protocol Registration Form must be hand delivered, faxed or e-mailed to the registrar at [name] or [[contact]](mailto:[contact]).*

Evaluating the effect of ADRB2 blockers on PKA/BAD/CREB signaling in the prostate gland

Wake Forest Baptist Comprehensive Cancer Center (WFBCCC)  
WFBCCC # 85716

**Appendix C – Perceived Stress**  
**Perceived Stress Scale – 4\***

**To be filled out by clinical staff**

**WISER PID:** \_\_\_\_\_ **Date Completed:** \_\_\_\_ / \_\_\_\_ / \_\_\_\_

**PI:** [name]., [name], D.V.M., Ph.D. **Study Number:** 8 5 7 1 6

**To be filled out by the patient:**

**Instructions:** This set of questions asks about your feelings over the **LAST 2 WEEKS.**  
Please indicate how often you have felt this way.

**Questions**

1. In the last 2 weeks, how often have you felt that you were unable to control the important things in your life?  
0 = Never  
1 = Almost Never  
2 = Sometimes  
3 = Fairly Often  
4 = Very Often
  
2. In the last 2 weeks, how often have you felt confident about your ability to handle your personal problems?  
0 = Never  
1 = Almost Never  
2 = Sometimes  
3 = Fairly Often  
4 = Very Often
  
3. In the last 2 weeks, how often have you felt that things were going your way?  
0 = Never  
1 = Almost Never  
2 = Sometimes  
3 = Fairly Often  
4 = Very Often
  
4. In the last 2 weeks, how often have you felt difficulties were piling up so high that you could not overcome them?  
0 = Never  
1 = Almost Never  
2 = Sometimes  
3 = Fairly Often  
4 = Very Often

\*Modified from:

Evaluating the effect of ADRB2 blockers on PKA/BAD/CREB signaling in the prostate  
gland

[figure not shown]
Wake Forest Baptist Comprehensive Cancer Center (WFBCCC)  
WFBCCC # 85716

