### **2.2 Secondary Objectives**

- 2.2.1 To compare activation of ADRB2/PKA/BAD signaling pathway in the prostate glands of men two hours after taking or not taking propranolol prior to prostate biopsy or prostatectomy as indicated by phosphorylated BAD.
- 2.2.2 To determine the difference in candidate transcript levels associated with ADRB2/PKA activation between individuals two hours after taking propranolol or not taking propranolol prior to prostate biopsy or prostatectomy.
- 2.2.3 To determine plasma propranolol levels in individuals taking propranolol two hours after administration prior to prostate biopsy or prostatectomy.
- 2.2.4 To determine if plasma catecholamine levels in men with prostate cancer can be used as a biomarker to identify patients who show activation of ADRB2 signaling pathway in prostate tumors.

- 2.2.5 To determine perceived stress level differences in men with prostate cancer prior to prostate biopsy or prostatectomy to examine possible association between perceived stress level and catecholamine levels in blood and activation of ADRB2 pathway in tumors
- 2.2.6 To determine perceived distress level differences in men with prostate cancer prior to prostate biopsy or prostatectomy to examine possible association between distress level and catecholamine levels in blood and activation of ADRB2 pathway in tumors.

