#### **4.2 Methods**

#### **Compare activation of ADRB2/PKA/BAD signaling pathway in the prostate glands of men who take or do not take ADRB2-selective beta blockers**

##### **Patients scheduled for prostate biopsy.**

The research staff screens the OR and clinic schedules for potential patients and provides a list to the investigator. [name] or co-Investigator will discuss the study with the patient and inform the research nurse or coordinator (research staff) about the patients who agreed to participate in the study. Research staff will inform Tissue Procurement Lab (Director [name]; [name], Tumor Procurement Coordinator) and courier about the scheduled date and time when prostate samples will be collected.

On the day of sample collection [name] lab will prepare box with dry ice for prostate biopsy samples, a box with wet ice for blood samples as well as 2 ml cryovials (Corning, cat#430488) to collect biopsies and tubes to collect blood (Na heparin, green-capped tube, 10 ml total blood volume).

Courier will pick up boxes from Tissue Procurement Lab (Director [name]; [name], [contact]) and deliver to research staff at Charlois clinic ([name]).

Recruited patients scheduled for prostate biopsy will be randomized into two groups. Group one will receive 40 mg propranolol given by research nurse 2 hours prior to prostate biopsy. The research nurse should withhold drug and contact treating physician if SBP <120 or HR < 63. Group two will receive no treatment.

All patients will fill out stress surveys on the biopsy day.

All patients will give approximately 10 mL of blood approximately 20 min prior to prostate biopsy to test plasma catecholamine levels (collected in 10 mL green top tube (sodium heparin) and sent on ice within 1 hour to clinical lab for processing) and propranolol level (collected in 10 mL green top tube (sodium heparin) and sent on ice to The Tissue Procurement lab for processing and storage as described below). For group one that takes propranolol, this blood sample will be drawn at 1.5 -2 hours after taking the propranolol tablet.

For the biopsy, at least 1 core of the prostate specimen is to be flash frozen (on dry ice -80C) for laboratory analysis. Each biopsy sample will be collected into separate cryovials. The samples will be picked up by courier at Charlois clinic and delivered to Tissue Procurement laboratory.. The tissue samples will be frozen at -80 C.

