### **Patients scheduled for prostatectomy.**

Research staff will inform Tissue Procurement Lab (Director [name]; [name], Tumor Procurement Coordinator) about the scheduled date and time when samples from prostate cancer patients will be collected at OR. Prior to the day of sample collection at specified time [name] lab will provide vials and freezing media to collect prostatectomy samples and plasma samples (Na heparin, green cup).

Recruited patients scheduled for prostatectomy will be randomized into two groups. Group one will receive 40 mg propranolol given by research staff 2 hours prior to prostatectomy. The research staff should withhold drug and contact the study physician performing the procedure and/or the anesthesiologist if SBP <120 or HR < 63. Group two will receive no treatment. All patients will fill out stress surveys prior to prostatectomy.

Research staff will collect stress questionnaire and will collect blood into the vials with Na heparin that will be stored on ice (+4C). All patients will give approximately 10 ml of blood approximately 20 min prior to prostatectomy to test plasma catecholamine levels and propranolol level. For group one that takes propranolol, this blood sample will be drawn at 1.5 -2 hours after taking the propranolol tablet. Blood will be collected into two 10 mL green top (sodium heparin) tubes. One tube will sent on ice within 1 hour to the clinical lab for processing of fractionated catecholamines. The other tube will be sent on ice to The Tissue Procurement lab for processing and storage. The plasma will be separated, transferred to cryovials, and stored in -80C at the Tissue Procurement Lab

Prior to anesthesia patient will be evaluated by anesthesiologist for hypotension and bradycardia. Prostatectomy samples will be collected by Tissue Procurement Coordinator and placed into cryovials and flash-frozen. At least 3 vials with the prostate specimens will be flash frozen (on dry ice -80C) for laboratory analysis and stored at the Tissue Procurement Lab.

Prostate samples will be analyzed for the overall status of prostate tissue (by pathologist) and for activation of ADRB2/PKA signaling pathway .

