**Experimental plan ([name] laboratory):**

1. Test whether LCM can be used to excise epithelial cells from frozen sections of prostate tissue for analysis of CREB and BAD phosphorylation by Western blotting, and for the analysis of mRNA by qPCR or RNA seq.
2. Recruit patients prior to prostate biopsy or prostatectomy. We plan to recruit 60 patients to this study and expect that 10 patients may not have evaluable tumor tissue. Patients will provide medical history and pre-study blood samples. On the day of prostate biopsy, the patients will fill out two stress surveys, being given propranolol or no treatment approximately 2 hours prior to biopsy or surgery, give blood, have prostate biopsy/prostatectomy, at which point prostate sample will be collected.
3. Compare CREB phosphorylation, BAD phosphorylation in prostates of men who took and who did not take propranolol. Based on our recent study of activation of ADRB2/PKA pathway in prostate biopsies we anticipate that in ~ 20% patients (10 of 50) ADRB2 pathway will be activated . If the selective beta blocker propranolol inhibits ADRB2/PKA pathway, then we will not see CREB and BAD phosphorylation in prostates of patients who take propranolol. In the no treatment group, patients are expected to show elevated BAD and CREB phosphorylation in their prostates. The levels of CREB and BAD phosphorylations will be determined by probing Western blots with antibodies to pS133CREB and total CREB; pS112BAD and total BAD. Ratios of signals from pS133CREB/total CREB and pS112BAD/total BAD will be used to compare CREB and BAD phosphorylations in prostate tissue samples.
4. Free plasma propranolol (pharmacologically active) will be measured at The Proteomics and Metabolomics Shared Resource (Dir. [name]) using chromatographic separation and fluorometric detection (linear detection range 5-400 µg/L) as described in .
5. Using prostate cancer cell models and tissues from the tumor bank, we will test if there is an mRNA signature of activation of ADRB2/PKA signaling pathway.

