#### **Experimental plan (clinical):**

Prior to prostate biopsy or prostatectomy, a complete history and physical will be performed per standard of care; this can be completed during the initial consult. The necessary clinical information, including most recent PSA and testosterone if available (per standard-of-care) will be retrospectively obtained from what is charted and recorded per Appendix G.

Study related activities for the day of prostate biopsy or prostatectomy should be recorded on the Surgery Day Worksheet (Appendix N). Patients will fill out both the perceived stress form (Appendix C) and the Distress Thermometer (Appendix D). Patients will receive either propranolol 40mg po x1 or no treatment 2 hours prior to prostate biopsy or prostatectomy. Approximately 20 minutes prior to prostate biopsy or prostatectomy, Group 1 will have approximately 10 mL of blood collected into two green top (sodium heparin) tubes. Group 2 will have the same amount of blood collected into two green tops. There will be no time limit prior to the biopsy or prostatectomy. Plasma will be separated and stored for future analysis of propranolol levels.

Epinephrine (fractionated catecholamines) levels will be performed per standard clinical laboratory procedures on all patients.

Information regarding tissue and plasma collection will be recorded on the Tissue Collection Form (Appendix H) or the Blood Collection Form (Appendix I). All stored plasma or tissue will be stored in the Tumor Tissue Core.

Tumor Tissue Core  
Wake Forest Baptist Comprehensive Cancer Center  
Tumor Tissue Core Facility  
Care of [name]  
[name]

[name]  
[name]

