## Appendix D – Distress Thermometer

WISER PID: \_\_\_\_\_ Date Completed: \_\_\_\_ / \_\_\_\_ / \_\_\_\_

PI: [name]., [name], D.V.M., Ph.D.

Study Number: 8 5 7 1 6

NCCN DISTRESS THERMOMETER
 
Instructions: Please circle the number (0–10) that best describes how much distress you have been experiencing in the past week including today.
 
Extreme distress
 		
NCCN National Comprehensive Cancer Network®
 
NCCN Distress Thermometer and Problem List for Patients
 
PROBLEM LIST Please indicate if any of the following has been a problem for you in the past week including today.
 
Be sure to check YES or NO for each.
 

YES	NO	Practical Problems	YES	NO	Physical Problems	

		Child care			Appearance	

		Housing			Bathing/dressing	

		Insurance/financial			Breathing	

		Transportation			Changes in urination	

		Work/school			Constipation	

		Treatment decisions			Diarrhea	

					Eating	

					Fatigue	

					Feeling swollen	

					Fever	

					Getting around	

					Indigestion	

					Memory/concentration	

					Mouth sores	

					Nausea	

					Nose dry/congested	

					Pain	

					Sexual	

					Skin dry/itchy	

					Sleep	

					Substance abuse	

					Tingling in hands/feet	

 
Family Problems
 

 Dealing with children

 Dealing with partner

 Ability to have children

 Family health issues

 
Emotional Problems
 

 Depression

 Fears

 Nervousness

 Sadness

 Worry

 Loss of interest in usual activities

 Spiritual/religious concerns

 
Other Problems: _____
	YES	NO	Practical Problems	YES	NO	Physical Problems			Child care			Appearance			Housing			Bathing/dressing			Insurance/financial			Breathing			Transportation			Changes in urination			Work/school			Constipation			Treatment decisions			Diarrhea						Eating						Fatigue						Feeling swollen						Fever						Getting around						Indigestion						Memory/concentration						Mouth sores						Nausea						Nose dry/congested						Pain						Sexual						Skin dry/itchy						Sleep						Substance abuse						Tingling in hands/feet

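### The two stress forms look back one to two weeks while catecholamines are a single pre-procedure value, so a null association in objectives 2.2.5 and 2.2.6 would not rule out a link with stress at the blood draw

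*Combined protocol and SAP*

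**What the plan says.** **Recall windows.** All four items of the Perceived Stress Scale-4 in Appendix C refer to the last two weeks; the first reads "In the last 2 weeks, how often have you felt that you were unable to control the important things in your life". The Distress Thermometer in Appendix D asks "how much distress you have been experiencing in the past week including today".

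**What the scores are related to.** Section 2.2 gives the purpose of objective 2.2.5 as "to examine possible association between perceived stress level and catecholamine levels in blood and activation of ADRB2 pathway in tumors", and of 2.2.6 as "to examine possible association between distress level and catecholamine levels in blood and activation of ADRB2 pathway in tumors".

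**When blood is taken.** Section 4.2 says for biopsy: "All patients will give approximately 10 mL of blood approximately 20 min prior to prostate biopsy to test plasma catecholamine levels". For prostatectomy it says: "All patients will give approximately 10 ml of blood approximately 20 min prior to prostatectomy to test plasma catecholamine levels and propranolol level". The clinical experimental plan repeats the 20 minutes for Group 1 but, after describing the Group 2 draw, adds: "There will be no time limit prior to the biopsy or prostatectomy". The laboratory experimental plan mentions an earlier sample ("Patients will provide medical history and pre-study blood samples") but gives it no assay or analysis.

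**When the forms are completed.** Outcomes 7.2.5 and 7.2.6 place both surveys on the day of surgery before propranolol. Appendix N lists both surveys, with the blood draw, under a heading for activities one to two hours after the drug in Group 1.

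**Planned analysis.** Section 8.3 specifies two-sample t-tests between arms and descriptive statistics. It specifies no correlation or regression of stress on catecholamines or pathway activation. No power is stated for 2.2.5 or 2.2.6.

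**The concern.** The rationale in Section 1.0 runs from stress to epinephrine to pathway activation. The epinephrine step is measured at one moment and the pathway in tissue taken shortly afterwards. The stress step is measured as an impression of the preceding one or two weeks. Nothing on the forms or the Surgery Day Worksheet records stress at the moment of the draw, and no text explains or acknowledges the different time frames.

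If pre-procedure epinephrine responds mainly to how the man feels while he waits, a recall score is a noisy stand-in for the relevant exposure and its association is diluted. A null could then mean either that stress at the draw is unrelated to catecholamines, or that the forms did not capture that stress. The data collected could not separate the two. A momentary rating cannot be recovered after the procedure, so the gap can be closed only before or during accrual.

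**Working it through.** **Is there a stated figure to reproduce?** Not for these objectives. The only power figure is for the primary endpoint in Section 8.1: 25 evaluable men per group, difference 0.21, SD 0.26, two-sided 0.05, 80% power. Noncentral-t power is 79.9%, so it reproduces. It does not bear on this point.

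**Time frames side by side**

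| Quantity | Period covered | Source |
|---|---|---|
| Perceived Stress Scale-4 | last 2 weeks | Appendix C |
| Distress Thermometer | past week, including today | Appendix D |
| Catecholamines | one draw, about 20 minutes before the procedure | Section 4.2 |
| Pathway activation | tissue taken at the procedure | Section 4.2 |
| Stress at the draw | not collected | Appendix N has no such line |

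**Illustration of dilution.** Inputs from the documents: 50 men with evaluable tissue and 60 enrolled (Sections 8.1 and 8.2). Two-sided 0.05 is carried over from the primary analysis. Inputs assumed, because the documents give neither: a correlation of 0.4 between epinephrine and stress at the draw, and a correlation ρ of 0.7, 0.5 or 0.3 between the recall score and stress at the draw. A further assumption is that the recall score relates to epinephrine only through stress at the draw.

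Observed correlation: r = 0.4 × ρ.

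Power by Fisher z: with m = atanh(r) × √(n − 3), power = Φ(m − 1.96) + Φ(−m − 1.96).

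Example, n = 50 and ρ = 0.5: r = 0.20, atanh(0.20) = 0.2027, √47 = 6.856, m = 1.390, power = Φ(−0.570) + Φ(−3.350) = 0.284 + 0.0004, or 28%.

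| ρ | Observed r | Power, n = 50 | Power, n = 60 |
|---|---|---|---|
| 1 (no dilution) | 0.40 | 83% | 89% |
| 0.7 | 0.28 | 50% | 58% |
| 0.5 | 0.20 | 28% | 33% |
| 0.3 | 0.12 | 13% | 15% |

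The n = 60 column suits stress with epinephrine, which needs no tissue. The n = 50 column suits stress with pathway activation, if the same correlations are assumed there.

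**Smallest correlation detectable with 80% power:** tanh((1.96 + 0.84)/√(n − 3)), which is 0.39 at n = 50 and 0.35 at n = 60.

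**What a null would still say.** The 95% interval around an observed r of 0 is about ± tanh(1.96/√(n − 3)): ±0.28 at n = 50 and ±0.25 at n = 60. That is a usable, if wide, bound on the association with recent background stress.

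**One arm alone.** At r = 0.4 with no dilution, power is 51% with 25 men (m = 0.4236 × √22 = 1.987) and 60% with 30 (m = 0.4236 × √27 = 2.201).

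**The case against.** The best defence is that the objectives speak of perceived stress and distress levels, not of acute stress. Section 1.0 cites chronic-stress work and patients living with increased stress, and Section 7.2 names these two instruments. Read that way, the forms measure what was intended. This stands as far as it goes. The documents do not say which kind of stress is meant, so a reader who infers that a null could not be interpreted at all goes too far: it would bear on recent background stress within the bounds above.

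Three other stronger readings are tempting and also unsupported.

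- That both forms miss the day of the draw. The Thermometer's window includes it, so the mismatch is weaker for 2.2.6 than for 2.2.5.
- That the forms could not register a calming effect of propranolol. This depends on when they are completed, and Sections 7.2.5 and 7.2.6 conflict with Appendix N on that. If the surveys follow the dose, the Thermometer could partly reflect it. In any case, no objective sets out to measure propranolol's effect on anxiety.
- That a drug effect within two hours proves that catecholamines and pathway state reflect only the last hours. Sustained stress could set the level that the drug then blocks.

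It is also fair to say that the assumed correlations have no anchor in the documents and that no association analysis is planned to which the power figures would apply. Both are true: the figures show how much dilution could matter, not how much there is.

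Finally, a momentary rating taken after dosing in Group 1 is a post-treatment variable, and a single item is a weaker instrument than a standard scale. That argues against replacing the existing forms, but not against adding the item.

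**Conclusion.** The point holds in a limited form. The Perceived Stress Scale-4, and to a lesser degree the Distress Thermometer, measure recent background stress, while the catecholamine level and the tissue are taken at or just before the procedure. With no momentary rating, a null association in 2.2.5 or 2.2.6 would not rule out a link with stress at the draw.

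The size cannot be fixed from the documents. For moderate to poor tracking of momentary stress by the recall score (0.7 down to 0.3), about two fifths to five sixths of the undiluted power is lost at n = 50 ((83 − 50)/83 = 40%; (83 − 13)/83 = 84%). This rests on the assumed correlation of 0.4 and on the recall score acting only through stress at the draw. If background stress has its own effect on epinephrine or the pathway, the loss would differ.

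This is a cheap improvement to two secondary objectives. The primary CREB comparison is untouched.

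**What to change.** 1. Add to Appendix N, beside the blood-draw time, one time-stamped item for both groups: distress right now, rated 0 to 10. Recording its time next to the draw time also helps because the 20-minute timing is not stated uniformly.
2. Keep the Perceived Stress Scale-4 and Distress Thermometer as the named measures for 2.2.5 and 2.2.6, and analyse the new item as an additional exposure.
3. Write the association analysis into Section 8.3: regress epinephrine, and separately the pCREB ratio, on stress with arm and an arm-by-stress interaction. An arm term alone is not enough, because a drug that blocks the pathway should change the slope as well as the mean. Report the no-treatment group estimate, which is free of any drug effect.
4. Reconcile Sections 7.2.5 and 7.2.6 (surveys before propranolol) with Appendix N (surveys under the post-drug heading).

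The cost is a few seconds per man and one REDCap field. The downsides are that the item is single and unvalidated, that it follows dosing in Group 1, and that precision within one arm is low: 51% to 60% power at r = 0.4 with 25 to 30 men. A null in the no-treatment group should therefore be reported with its interval and not read as absence of a link.

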## Appendix D – Distress Thermometer

WISER PID: \_\_\_\_\_ Date Completed: \_\_\_\_ / \_\_\_\_ / \_\_\_\_

PI: [name]., [name], D.V.M., Ph.D.

Study Number: 8 5 7 1 6

NCCN DISTRESS THERMOMETER
 
Instructions: Please circle the number (0–10) that best describes how much distress you have been experiencing in the past week including today.
 
Extreme distress
 		
NCCN National Comprehensive Cancer Network®
 
NCCN Distress Thermometer and Problem List for Patients
 
PROBLEM LIST Please indicate if any of the following has been a problem for you in the past week including today.
 
Be sure to check YES or NO for each.
 

YES	NO	Practical Problems	YES	NO	Physical Problems	

		Child care			Appearance	

		Housing			Bathing/dressing	

		Insurance/financial			Breathing	

		Transportation			Changes in urination	

		Work/school			Constipation	

		Treatment decisions			Diarrhea	

					Eating	

					Fatigue	

					Feeling swollen	

					Fever	

					Getting around	

					Indigestion	

					Memory/concentration	

					Mouth sores	

					Nausea	

					Nose dry/congested	

					Pain	

					Sexual	

					Skin dry/itchy	

					Sleep	

					Substance abuse	

					Tingling in hands/feet	

 
Family Problems
 

 Dealing with children

 Dealing with partner

 Ability to have children

 Family health issues

 
Emotional Problems
 

 Depression

 Fears

 Nervousness

 Sadness

 Worry

 Loss of interest in usual activities

 Spiritual/religious concerns

 
Other Problems: _____
	YES	NO	Practical Problems	YES	NO	Physical Problems			Child care			Appearance			Housing			Bathing/dressing			Insurance/financial			Breathing			Transportation			Changes in urination			Work/school			Constipation			Treatment decisions			Diarrhea						Eating						Fatigue						Feeling swollen						Fever						Getting around						Indigestion						Memory/concentration						Mouth sores						Nausea						Nose dry/congested						Pain						Sexual						Skin dry/itchy						Sleep						Substance abuse						Tingling in hands/feet
YES	NO	Practical Problems	YES	NO	Physical Problems																																																																																																																																							
		Child care			Appearance																																																																																																																																							
		Housing			Bathing/dressing																																																																																																																																							
		Insurance/financial			Breathing																																																																																																																																							
		Transportation			Changes in urination																																																																																																																																							
		Work/school			Constipation																																																																																																																																							
		Treatment decisions			Diarrhea																																																																																																																																							
					Eating																																																																																																																																							
					Fatigue																																																																																																																																							
					Feeling swollen																																																																																																																																							
					Fever																																																																																																																																							
					Getting around																																																																																																																																							
					Indigestion																																																																																																																																							
					Memory/concentration																																																																																																																																							
					Mouth sores																																																																																																																																							
					Nausea																																																																																																																																							
					Nose dry/congested																																																																																																																																							
					Pain																																																																																																																																							
					Sexual																																																																																																																																							
					Skin dry/itchy																																																																																																																																							
					Sleep																																																																																																																																							
					Substance abuse																																																																																																																																							
					Tingling in hands/feet																																																																																																																																							

Version 1.2/2016, US/06/16. The NCCN Clinical Practice Guidelines (NCCN Guidelines®) are a statement of evidence and consensus of the authors regarding their views of currently accepted approaches to treatment. Any clinician seeking to apply or consult the NCCN Guidelines is expected to use independent medical judgment in the context of individual clinical circumstances to determine any patient's care or treatment. The National Comprehensive Cancer Network® (NCCN®) makes no representations or warranties of any kind regarding their content, use or application and disclaims any responsibility for their application or use in any way. The NCCN Guidelines are copyrighted by National Comprehensive Cancer Network®. All rights reserved. The NCCN Guidelines and the illustrations herein may not be reproduced in any form without the express written permission of NCCN. © 2016.

Evaluating the effect of ADRB2 blockers on PKA/BAD/CREB signaling in the prostate gland  
Wake Forest Baptist Comprehensive Cancer Center (WFBCCC)  
WFBCCC # 85716

